Because we have no a priori hypothesis of equivalence between treatment arms on these outcomes, these analyses will be conducted using standard hypothesis testing principles. We will report the mean (for continuous measures) or frequency (for binary measures) and 95% CIs for each measure within treatment arms as well as the difference in means or frequencies between treatment arms and the 95% CI of the difference. Secondary outcomes will be measured with a frequency as described in Appendix D, Schedule of Study Procedures. We will analyze these measures using linear or logistic regression models with robust variance estimators via Generalized Estimating Equations (GEE) to account for within-patient correlation that occurs with repeated measures. Regression models will include terms for treatment arm, time since randomization (categorical), skin type, and the treatment arm/time interaction. Inclusion of the interaction term will allow us to assess possible variation in effectiveness of home phototherapy relative to office-based phototherapy over time. Physician reported outcomes (PGA times BSA) will be measured at baseline and at the earlier of week 12 or upon discontinuation of phototherapy, whichever comes first. We will compare this outcome between home and office-based phototherapy arms using linear regression adjusted for skin-type. All secondary analyses will be repeated within each skin type stratum.

During the follow-up observation period, weeks 13-24 after start of therapy, we will compare dichotomized DLQI, and receipt of concomitant topical psoriasis treatment between study arms. These measures will be assessed every four weeks during the observation period and analyses will use the same approach as described above for other secondary outcomes. We will also assess change in oral or biologic psoriasis treatment during the observation period at week 24.

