8.3 Sample Size and Power Determination

Our study has been powered to allow us to determine non-inferiority of effectiveness both overall and within two of the three skin type strata. Because a clinical question is whether effectiveness is equivalent within each skin type sub-group, our sample size has been determined in order to provide adequate power for these skin type-specific analyses. We have pre-specified two primary effectiveness outcomes and assume a type I error rate for each outcome at the one-sided alpha = 2.5% level which is standard for a non-inferiority trial and analogous to the more familiar two-sided alpha = 0.05. Although this alpha level does not explicitly account for multiple comparisons, we believe that doing so would be unnecessarily conservative as both our patient-reported and physician-reported outcome measures assess the same outcome and are expected to be very highly correlated⁴⁶. Assuming a 50% response rate in both the office based phototherapy group and the home-based group and a non-inferiority margin of 15% (i.e. the 95% two-sided confidence interval on the difference in response rates between office and home-based groups excludes 15%), we calculated that 175 patients of each skin type would need to be included in each study arm to have 80% power to establish non-inferiority of home based phototherapy at a one-sided significance level of 2.5%. In the pooled sample, we will have 99% power for a non-inferiority

margin of 15%. Our non-inferiority margin has been iterated with our patient research partners and expert dermatologists. It is well within previous suggestions of non-inferiority for psoriasis treatments⁴⁷. We also note that the FDA accepts a 15% margin or greater for the study of biosimilars of biologics for moderate to severe psoriasis^{48, 49}. Additionally, our estimates are more conservative (i.e., require a larger sample size) than the non-inferiority margin specified in the pragmatic trial of home versus office based phototherapy conducted in the Netherlands which only required 100 patients per group total³⁰. Our estimates require a larger sample size compared to the Netherlands study primarily because we have set a higher bar for effectiveness. Based on preliminary data, the rate of DLQI ≤5 is anticipated to be similar to the estimate of achieving clear or almost clear skin, providing 80% power for the same non-inferiority margin for this outcome¹⁵.

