8.4.5 Missing Data Strategy

Our analysis strategy for the primary outcome of clear/almost clear skin and the patient reported DLQI (no impact on quality of life) uses an ITT strategy by treating all patients who discontinue treatment prior to achieving clear/almost clear skin as treatment failures. Thus, for these outcomes there will be no missing data. For secondary and exploratory analyses of longitudinal outcome measures that require data from follow-up assessments, such as dosing of phototherapy, frequency of concomitant psoriasis treatment, and amount of time spent on treatment, our analysis strategy incorporates all available baseline and longitudinal information. The GEE estimator is only unbiased if data are missing completely at random (MCAR). If the total proportion of observations with missing data in a given analysis exceeds 10%, we will address loss of efficiency due to missing data and possible bias arising from violation of the assumption of MCAR missingness by undertaking multiple imputation (MI) implemented using multiple imputation via chained equations (MICE). Using MICE, we will create 10 imputed versions of the complete data set with all missing outcomes and patient characteristics imputed simultaneously. For each analysis that makes use of data elements with missingness, we will then conduct the analysis in each imputed data set and combine the results using standard rules.

We will conduct additional sensitivity analyses to explore the sensitivity of our results to possible missing not at random missingness. We will use the "tipping-point" approach to identify combinations of values for missing measures that would change the conclusion of our study and will summarize the results using graphical displays.

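### Section 8.4.5 fixes multiple imputation at 10 data sets, with no seed or Monte Carlo error check, so secondary and exploratory results carry more simulation noise than they need to

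*Combined protocol and SAP*

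**What the plan says.** Section 8.4.5 sets out the missing-data strategy. Both co-primary outcomes are handled by counting non-completers as failures: "Thus, for these outcomes there will be no missing data". Multiple imputation by chained equations belongs to a different group: "For secondary and exploratory analyses of longitudinal outcome measures that require data from follow-up assessments". It is conditional: "If the total proportion of observations with missing data in a given analysis exceeds 10" percent, imputation is carried out. No upper bound on missingness is mentioned. The number of data sets is then fixed: "Using MICE, we will create 10 imputed versions of the complete data set". The analyst is to "combine the results using standard rules", which I take to mean Rubin's rules.

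For the secondary outcomes, section 8.2 states that "these analyses will be conducted using standard hypothesis testing principles", with 95% confidence intervals for the arm differences. It lists 11 such outcomes and repeats all secondary analyses within each skin type stratum. Neither section names a random seed or a limit on Monte Carlo error. The tipping-point analysis in 8.4.5 concerns data missing not at random, which is a different question.

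**The concern.** Imputation starts only once missingness is already appreciable, yet the number of imputed data sets stays at 10 however much is missing. Choosing 10 is usually defended on efficiency, because little precision is lost. Efficiency does not measure repeatability. With few imputations, the same data and the same model give different estimates, intervals and p-values under different seeds. With 11 secondary outcomes, several of them longitudinal and all repeated by skin type, a result near 0.05 is plausible. A reader of that result could not tell whether another run would have agreed with it.

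**Working it through.** **The plan's own figure.** The documents give no figure for imputation error, so the only calculation to reproduce is the sample size in 8.3: "Assuming a 50% response rate in both the office based phototherapy group and the home-based group", a margin of 15 points and one-sided 2.5%. n per arm = (1.960 + 0.842)² × (0.25 + 0.25) / 0.15² = 174.4, that is 175, which agrees. Power is 80.1% at 175 per arm and 99.8% at 525 per arm. None of this involves imputation.

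**Inputs.** From 8.4.5: m = 10, trigger above 10%, no upper bound. From 8.2: standard tests and 95% CIs, taken as two-sided 0.05. Assumed: FMI of 0.05, 0.1, 0.2 and 0.3, because the documents give neither FMI nor expected missingness.

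**Step 1, efficiency.** Relative efficiency = 1/(1 + FMI/m). At m = 10 this is 99.5% for FMI 0.05 and 97.1% for FMI 0.3, so the loss is small.

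**Step 2, noise in the estimate.** Monte Carlo SD / SE = √(FMI/m). At m = 10: √0.005 = 0.071, √0.01 = 0.100, √0.02 = 0.141, √0.03 = 0.173. At m = 100: 0.022, 0.032, 0.045, 0.055.

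**Step 3, noise in the p-value.** I simulated repeated runs on one data set whose infinite-imputation statistic is z. In each run the pooled estimate is drawn as z plus normal noise with variance FMI/m. The between-imputation variance is drawn as FMI × χ²/(m − 1) on m − 1 degrees of freedom. The p-value uses Rubin's total variance and t degrees of freedom. The second column gives the central 95% range of p when the stable p is 0.05. The last three give the chance that two seeds disagree on p<0.05 when the stable z is 2.1 (p = 0.036).

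| FMI | p range, m = 10 | Disagree, m = 10 | m = 50 | m = 100 |
|---|---|---|---|---|
| 0.05 | 0.036–0.071 | 7% | 0% | 0% |
| 0.1 | 0.030–0.083 | 23% | 0.5% | under 0.1% |
| 0.2 | 0.023–0.109 | 39% | 7% | 1% |
| 0.3 | 0.018–0.135 | 45% | 17% | 5% |

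As a cross-check, one simulated data set of 780 patients was imputed directly 400 times at m = 10, with a stable z of about 2.0. The 95% range of p was 0.029–0.075 with 10% missing and 0.016–0.119 with 25% missing, in line with the table.

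**Step 4, averaged over where z falls.** The table conditions on a borderline result. Drawing z at random instead, with m = 10 and FMI 0.05 to 0.3, two seeds disagree on p<0.05 in about 1% to 3% of analyses under no effect and 2% to 8% at 80% power (noncentrality 2.8). For a clear effect (noncentrality 4) the figure is below 2%.

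**Step 5, validity.** In the same simulation the type I error at m = 10 was about 5% throughout. Where power is nominally 80%, at FMI 0.3 it was 77.9% with 10 imputations and 79.8% with 100, a difference of about 2 points.

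**Step 6, imputations needed for a 6% limit.** m = FMI/0.06²: 14 at FMI 0.05, 28 at 0.1, 56 at 0.2 and 84 at 0.3.

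**The case against.** The strongest reply is that nothing here is wrong, only less precise than it could be. Rubin's variance already includes the between-imputation variance divided by m, and the t reference allows for small m, so tests and intervals keep their stated properties. That stands. A reader might infer that 10 imputations bias the secondary results or inflate their error rate; step 5 shows that they do not.

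A reader might also infer that the non-inferiority conclusion could turn on the seed. The documents rule this out: non-completers count as failures on both co-primary outcomes, which therefore never enter the imputation. Sections 8.2 and 8.4.5 also attach no decision rule to the imputed secondary outcomes, so crossing 0.05 on one of them settles nothing about the trial.

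It is fair, too, that 39% or 45% disagreement describes only a result that happens to lie near the threshold; the averages in step 4 are much lower. Nor does the 10% trigger imply an FMI above 0.1. The trigger counts missing observations, while 8.4.5 draws on all available baseline and longitudinal data, and DLQI is collected every four weeks, so FMI can fall below the missing proportion. That is why the range here starts at 0.05.

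Finally, more imputations do not abolish the problem. With a stable z of 2.0 and FMI 0.1, two seeds still disagree in 23% of pairs at m = 100. A fixed seed makes a run repeatable but does not reduce its error.

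After all this, one point remains: the noise serves no purpose and is cheap to reduce.

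**Conclusion.** The point holds as a low-priority improvement confined to secondary and exploratory analyses that trigger imputation. On an assumed FMI of 0.05 to 0.3, raising m from 10 to 100 cuts the Monte Carlo SD from 7–17% of the standard error to 2–5.5%. It also cuts seed disagreement for a result at z = 2.1 from 7–45% to 0–5%. Clear results, in either direction, hardly move. The size depends on the FMI assumption, on Rubin's rules being the intended combination method, and on a two-sided 0.05 threshold. The documents confirm none of these explicitly.

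**What to change.** In section 8.4.5, replace the fixed 10 in one of two ways: state a larger number, for example 100, or set the number for each analysis so that the Monte Carlo error of the treatment estimate is below about 6% of its standard error. Either is sufficient. The second needs fewer imputations when FMI is low and more than 100 when it is high (0.4/0.06² = 111.1, so 112 at FMI 0.4). In addition, pre-specify the random seed so that the reported run can be repeated. The cost is a line of SAP wording and a little computing time, with no change to data collection, sample size or the primary analysis.

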8.5 Subject Population(s) for Analysis

The primary analysis will be based on all subjects randomized into the study, regardless of whether they received the assigned treatment. We will also conduct an "as treated" analysis in order to evaluate those who completed the study and received at least 80% of treatments

9 Safety and Adverse Events

Designated site personnel at each site have the front-line responsibility of reviewing patient-reported response to phototherapy, identifying and documenting treatment emergent adverse events, and adjusting phototherapy dosing accordingly. The Sponsor/Study Principal Investigator is responsible for tracking these reports and relaying them, if required, to the IRBs and other investigators. For this pragmatic study, where intervention is standard of care and performed by the patient's clinician or the patient themselves (in the case of home treatment), AE's not related to phototherapy are not required to be recorded or followed by patient's clinician and will not be recorded for study purposes.

9.1 Definitions

9.1.1 Adverse Event

An **adverse event** (AE) is any symptom, sign, illness or experience that develops or worsens in severity during the course of the study. For the purpose of this pragmatic trial, for which the intervention occurs during standard of care visits, we will only record and collect data on adverse events that are specifically related to phototherapy treatment, except for serious adverse events which will be collected regardless of relationship to phototherapy.

9.1.2 Serious Adverse Event

Serious Adverse Event

Adverse events are classified as serious or non-serious. A serious adverse event is any AE that is:

- fatal
- life-threatening
- requires or prolongs hospital stay

- results in persistent or significant disability or incapacity
- a congenital anomaly or birth defect
- an important medical event

Important medical events are those that may not be immediately life threatening, but are clearly of major clinical significance. They may jeopardize the subject, and may require intervention to prevent one of the other serious outcomes noted above. For example, drug overdose or abuse, a seizure that did not result in in-patient hospitalization or intensive treatment of bronchospasm in an emergency department would typically be considered serious.

All adverse events that do not meet any of the criteria for serious should be regarded as non-serious adverse events.

9.2 Recording of Adverse Events

This pragmatic trial will be evaluating the effectiveness of two standard of care treatments, home and office-based phototherapy. All treatments will be administered and monitored by the patient's clinical care provider (dermatologist) and designated staff (typically phototherapy nurses). Recording of reported adverse events will be completed by the patient's clinical care provider(s) prior to the administration of each treatment (3 times per week) and the clinical course of each event will be followed until resolution, stabilization, or until it is determined that phototherapy is not the cause. Adverse events will be documented in the patient's medical record by the clinical care provider(s) throughout the 12 week intervention period and the subsequent 12 week observation period per local practice or medical center requirements. Only phototherapy-emergent adverse events will be abstracted from medical records and/or home phototherapy equipment and recorded for study objective purposes.

Serious adverse events will be recorded and monitored by the patient's clinical care provider(s), per standard of care practices, and will also be recorded, tracked, and reported by the study in the appropriate case report form and SAE reporting form at Visit 2. Serious adverse events that are identified at the end of the study intervention period will be followed up to determine the final outcome. Any serious adverse event that occurs after the study intervention period and is considered to be possibly related to the study intervention or study participation will be recorded and reported immediately.

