1.2.3 Clinical Studies in Children

Phototherapy is generally effective and safe in children and is considered standard of care for the treatment of pediatric psoriasis;³¹⁻³⁴ however, prospective trials are very limited. To date, there have been 2 prospective studies of office-based UVB therapy in pediatric patients with psoriasis. Twenty children between the ages of 6 and 14 years old were enrolled in a single-center trial of twice weekly NB-UVB in a dermatology clinic in India, with 12 (60%) showing PASI 90, 3 (15%) showing PASI 70-90, 1 (5%) showing PASI 50-70, and 2 (10%) showing less than PASI 50 or worsening disease after 12 weeks³⁵. The only reported adverse event was mild erythema in 2 (10%) patients. The same center also performed a prospective single-blinded trial comparing twice weekly NB-UVB versus NB-UVB with mineral oil pretreatment in a split-body design; of the 18 patients analyzed, both groups had large reductions in the mean modified PASI score (mean baseline score of 15.3 to scores of 0.64 and 0.14 at 12 weeks in the NB-UVB and NB-UVB mineral oil pretreated groups, respectively)³⁶.

The majority of efficacy and safety data for UVB use in pediatric psoriasis in the literature are based on retrospective reviews. In one of the largest reviews to date, 79 children with psoriasis were treated with NB-UVB at a single institution in Israel between 1998-2006; among them, 40 (51%) achieved complete clearance, 33 (41%) at least 75% improvement, and 6 (8%) less than 75% improvement. Side effects were minor and included 13 (15%) patients with mild erythema, 2 (1%) with itch, and 3 (3%) with burning³⁷. In other smaller retrospective reviews, response rates have ranged from 63-88% of patients achieving clear or almost clear skin; 45-86% of patients achieving 90% improvement in PASI or BSA; 17-40% of patients achieving 70-90% improvement in PASI or BSA; 20-22% of patients achieving 50-70% improvement in PASI; and 9-15% of patients with minimal or no improvement³⁸⁻⁴³. There have been no published studies of home UVB phototherapy for pediatric psoriasis; however, home phototherapy is widely accepted by US dermatologists for the treatment of children with psoriasis and other light responsive disorders.

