3.2.3 Primary Safety Endpoints

The primary safety outcome is the proportion of patients reporting treatment-emergent adverse events. Adverse events include patient reported burns and their severity. Patients will be queried about these events immediately prior to each phototherapy treatment by the clinical staff (for patients assigned to office base phototherapy) or by the home phototherapy machine. We will also evaluate all serious adverse events regardless of their relationship to treatment. All patients will be queried about SAEs by the sites at the visit 2. Patients can spontaneously report SAEs at any point during the study.

4 Study Population and Duration of Participation

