6.2 Study Intervention Phase Weeks 1-12

6.2.1 Week 1

- Administer NB-UVB phototherapy three times per week
- Patient reported DLQI (complete prior to first phototherapy treatment)
- Patient reported target lesion image taken prior to first treatment
- Patient reported psoriasis topical treatment
- Patient reported response to phototherapy prior to treatments. For those on office treatment, data is entered by the sites. For those on home treatment, data is recorded on the home device.
- Phototherapy session number and dose. For those on office treatment, data is entered by the sites. For those on home treatment, data is recorded on the home device

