6.5.1 Data Collection and Follow-up for Withdrawn or Early Termination Participants

Participants who withdraw consent to participate in the study will be asked to report the reason for withdrawal.

7 Study Evaluations and Measurements

The data collected in this study are all considered relevant for routine clinical care. In routine clinical care, there is some variation in which assessments are conducted and thus we will standardize assessments for the purpose of the study.

Investigator reported measures:

1. Physicians Global assessment (PGA): This is a three item measure that asks the physician or his or her designee to assess the thickness, redness, and scale of psoriasis plaques.

2. Body Surface Area (BSA): This is a measure that asks the physician or his or her designee to assess the body surface area affected by psoriasis using the handprint method in which the palm of the entire hand approximates 1% of the body surface area. To do this, the patient's handprint, including the entire area of the palm and all 5 digits with the fingers close together but not overlapping, is used as a guide to estimate 1% of the BSA

3. Number of phototherapy treatments and dose received: This data is routinely collected in clinical practice. It will be reported by the sites for patients receiving office treatment and will be obtained from the machines for those receiving home based treatment

- 4. Copay for office-based phototherapy
- 5. Concomitant treatment

Patient reported measures:

1. Dermatology Life Quality Index: (DLQI): DLQI is a 10 item survey that asks patients questions about their health related quality of life on a 0-3 scale. DLQI is routinely used in clinical trials of psoriasis treatments and can also be used routinely in clinical practice.

2. Patient reported response to phototherapy: This is a standard question asked to the patient to document the degree and duration of erythema induced by the prior phototherapy treatment session. It is standard of care.

- 3. Patient reported time spent on travel, cost of travel, and time spent on phototherapy
- 4. Patient reported concomitant psoriasis topical treatment

5. Photograph of target psoriasis lesion (at a subset of study sites)

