8.4.3 Safety Analysis

The primary safety outcome is the proportion of patients reporting treatment-emergent adverse events. Adverse events include patient reported burns and their severity. We hypothesize that safety of home based UVB phototherapy will not be different from office based phototherapy. We anticipate based on extensive experience, that the number of clinically significant burns (i.e., which may require the patient to seek advice from the treating physician and occur due to human error) will be rare (affecting <1% of patients) and typically can be managed at home with over the counter remedies.

As ultraviolet light does not have adverse effects beyond the skin, our stakeholders believe that safety assessments should focus on skin related events such as burns and serious adverse events. We will summarize the number, severity, and type of adverse events experienced by patients in each treatment arm. We will compute the proportion of patients experiencing adverse events by treatment arm, with 95% CI. Similar to analyses for our effectiveness outcomes, we will also fit skin type-adjusted logistic regression models and use standardization to estimate adjusted risk differences between treatment arms. In addition to pooled safety analyses, we will also compare the proportion of patients experiencing adverse events between office-based and home-based phototherapy arms within each skin type sub-group

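### The primary safety proportion pools staff-queried and charted events in the office arm with machine self-report at home, and the plan does not say how the two will be made comparable

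*Combined protocol and SAP*

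**What the plan says.** Section 8.4.3 states: "The primary safety outcome is the proportion of patients reporting treatment-emergent adverse events". Burns and their severity are included but are not the whole outcome. The analysis is a direct contrast: "We will compute the proportion of patients experiencing adverse events by treatment arm, with 95% CI", followed by skin-type-adjusted risk differences and comparisons within each skin type.

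Section 3.2.3 says patients are asked about these events before each session "by the clinical staff (for patients assigned to office base phototherapy) or by the home phototherapy machine". Section 6.2 repeats the split for the patient-reported response item: "For those on office treatment, data is entered by the sites. For those on home treatment, data is recorded on the home device". Section 7 describes that item, once and for all patients, as a standard question "to document the degree and duration of erythema induced by the prior phototherapy treatment session". Section 7.6 likewise describes the pre-session query as being about burns.

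Section 9.2 adds a second stream. Providers record reported events before each treatment and document them in the chart through the intervention and observation periods. Then: "Only phototherapy-emergent adverse events will be abstracted from medical records and/or home phototherapy equipment and recorded for study objective purposes". The same section says that all treatments are administered and monitored by the care provider and staff, whereas the opening of section 9 says that home treatment may be performed by the patient.

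**The concern.** A difference in proportions means something only if both arms had a similar chance of having an event noticed and recorded. Here one arm has a staff interview and a charting opportunity at up to 36 sessions (section 5.7), and the other has self-entry on a device. If phototherapy-related reactions outside the erythema item are mentioned and charted more readily in the office, home treatment will look safer at equal true risk, or a real home excess will be partly hidden.

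This bears on the purpose of the trial. Section 1.1 cites uncertainty about the safety of home units as a reason for reluctance to prescribe them, and section 1 anticipates possible tolerability differences in skin types I/II. No planned analysis covers the problem. The tipping-point analysis in section 8.4.5 varies missing values, not events that nobody asked about.

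**Working it through.** **Step 1: sources for non-serious, phototherapy-related events, by arm**

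| Source | Office | Home |
|---|---|---|
| Pre-session response item (3.2.3, 6.2, 7, 7.6) | Asked by staff, entered by site | Asked by machine, stored on device |
| Provider recording before each treatment (9.2) | Possible at each session | Not possible as written; the patient gives the treatment (9) |
| Site review of patient-reported responses (9) | Yes | Yes, but only of what was asked |
| Patient-initiated contact (7.6) | For significant reactions | Same |
| Skin examination at visit 2 (7.2) | Yes | Yes |
| Query at visit 2 (3.2.3, 6.2.5) | Serious events only | Serious events only |
| Four-weekly patient-reported items (6.2, 6.3) | DLQI, image, topical treatment | Same; no skin-reaction item |

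The arms differ in the first two rows, and section 9.2 lets both rows feed one proportion. Nothing in the lower rows asks either arm systematically about non-serious reactions, so nothing there offsets the difference.

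**Step 2: what unequal capture could do**

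The plan states no sample size, power or margin for safety, so there is no figure to reproduce. It gives no rate for non-erythema reactions and no capture fractions. The figures below are assumptions.

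Inputs: n = 1050/2 = 525 per arm (section 4.5); true risk p of a non-erythema phototherapy-related reaction, equal in both arms; full office capture; home capture fraction c. The proportion examined consists of these reactions alone.

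- Home observed: h = p × c. Spurious difference: d = p − h.
- SE0 = √[2·p̄(1−p̄)/n], with p̄ = (p+h)/2. SE1 = √[p(1−p)/n + h(1−h)/n].
- Chance of a two-sided 5% result falsely favouring home: Φ[(d − 1.96·SE0)/SE1]. With equal capture this is 2.5%.

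For p = 5%:

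- c = 75%: h = 3.75%, d = 1.25 points, SE0 = SE1 = 1.262 points. (1.25 − 1.96 × 1.262)/1.262 = −0.970, so Φ = 0.166.
- c = 50%: h = 2.5%, d = 2.5 points, SE0 = 1.173 and SE1 = 1.170 points. (2.5 − 1.96 × 1.173)/1.170 = 0.172, so Φ = 0.568.

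**Step 3: range**

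Section 3.1 anticipates only about 80 patients of skin type V/VI. That gives (350 + 350 + 80)/2 = 390 per arm, shown alongside.

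| True risk | Home capture | Difference (points) | Chance, 525 per arm | Chance, 390 per arm |
|---|---|---|---|---|
| 1% | 75% | 0.25 | 6% | 6% |
| 1% | 50% | 0.5 | 15% | 13% |
| 5% | 75% | 1.25 | 17% | 13% |
| 5% | 50% | 2.5 | 57% | 45% |
| 10% | 75% | 2.5 | 30% | 23% |
| 10% | 50% | 5.0 | 87% | 76% |

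In the all-event proportion, erythema events add variance, and a patient with both erythema and another reaction still counts at home. The chances there would be lower for the same capture gap.

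**The case against.** The routes are openly stated and follow from comparing two settings pragmatically. The erythema item is listed for both arms and differs only in how it is entered. Non-serious events count only if related to phototherapy, in either arm (sections 9, 9.1.1, 9.2, 9.3). Home patients can also reach the chart: they are told to contact clinicians for significant reactions, site staff review their responses, and the skin is examined at visit 2. The phototherapy-response questionnaire is listed under Appendix E, but its text is not in the material available, so the exact wording put to each arm cannot be compared.

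All of that stands, and it rules out three stronger readings. A reader might infer that office patients are asked about adverse events of any kind while home patients get only an erythema question. The documents contradict the first half and do not support the contrast. A reader might infer that events are certainly under-counted at home. That is an inference, and for erythema itself staff interview versus self-entry could shift the count either way. A reader might also take a size from the series in section 1.2.3, whose side effects "included 13 (15%) patients with mild erythema, 2 (1%) with itch, and 3 (3%) with burning". It is a retrospective, single-institution paediatric review whose counts and percentages disagree (13/79 is 16.5%, not 15%). Applying it would also need full office capture, no home capture of non-erythema events and no patient with two event types. It is not a basis for an estimate here.

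The objection does not remove the second row of the table in the working. Provider charting before each session exists in one arm only and enters the same proportion.

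**Conclusion.** The concern holds in this form. Phototherapy-related adverse events are ascertained by different routes in the two arms, section 9.2 describes a recording step that does not fit home treatment, and section 8.4.3 compares the pooled result as one measure. Under-capture at home is plausible for non-erythema reactions below the threshold at which patients are told to call. The direction for erythema is unknown, so the net direction is not established.

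The size cannot be derived from the documents. The illustration of 1.25 to 2.5 points, with a 17% to 57% chance of a false finding for home, rests on an assumed 5% risk, full office capture, 50% to 75% home capture, 525 per arm, and a proportion made up of these reactions alone. At 1% risk the distortion is small; at 10% with half captured it would usually produce a false finding. The plan should be changed, because the bias would not shrink with sample size and the change is cheap.

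**What to change.** 1. In sections 3.2.3 and 8.4.3, base the primary between-arm safety comparison on the pre-session response item asked in both arms, with the same response options and the same cut-off for counting a burn.
2. Report chart-abstracted events descriptively by arm and source, and give the all-source proportion as a sensitivity analysis.
3. Add one identical, self-completed skin-reaction item to the existing four-weekly app survey in both arms, as a supporting comparison for reactions other than erythema.
4. Reconcile sections 3.2.3, 7, 7.6, 9 and 9.2 on who records adverse events for home patients and what is asked.

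The cost is protocol and SAP wording plus one item in a survey that patients already complete. There are three downsides. The new item carries four-week recall. The pre-session item still differs by mode (staff interview against machine entry). The primary compared proportion becomes narrower than all treatment-emergent adverse events.
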